### 13.3 Stratification Factors

BM samples from patients will be analyzed for NRAS, KRAS, BRAF mutations (next generation sequencing) at baseline visit. Patients will be stratified into one of two study groups as strategy for biomarker-based patient enrichment:

- Biomarker positive (NRAS, KRAS, BRAF mutated as defined [Appendix F](#))
- Biomarker negative (without NRAS, KRAS, BRAF mutation)

Patients in both groups will receive 2.0 mg daily oral trametinib. Each group will enroll 12 patients in the first stage and an additional 25 patients in the second stage, if the pre-determined response criteria are met during the first phase.

### 13.4 Analysis of Secondary Endpoints

**The secondary objectives are to:**

- To evaluate progression free survival (PFS) and duration of response (DOR) in the two stratified groups
- To document ORR after the addition of GSK2141795 to trametinib in patients who have developed progressive disease or have achieved less than a partial response (PR) after 4 cycles of treatment
- To evaluate PFS and DOR in patients receiving trametinib plus GSK2141795
- To evaluate the safety profile of trametinib with and without GSK2141795

The endpoints for secondary objectives, ORR is defined in sections [13.1](#) and [13.5.2](#) and will employ the M-protein level at the time of addition of GSK2141795 as the new baseline for response assessment.

Safety analyses will review adverse events, electrocardiogram results, laboratory tests (hematology, clinical chemistry, and coagulation test), vital signs and physical examinations. Any patient who receives any amount of the study drug will be evaluated for toxicity. Safety will be measured in terms of type, frequency and severity of adverse event reactions reported according to CTCAE v4.0.

PFS will be evaluated as defined by the time from the date of start of treatment to the date of documented progression (based on IMWG criteria) or death due to any cause. For patients who are not known to have died and who do not have objective evidence of tumor progression, and who are either removed from study treatment or who are given antitumor treatment other than the assigned study treatment, PFS will be censored at the last complete disease assessment. Patients who complete the study and have not progressed at the cut-off date for final analysis will be censored at the last complete disease assessment. Patients with two or more missing assessments immediately prior to the next visit with a documented progression will be censored for PFS at the last assessment with documentation of no progression.

The DOR is measured from the time measurement criteria are met for CR or PR (whichever is first recorded) until the first date that recurrent or progressive disease is objectively documented or to death due to multiple myeloma (taking as reference for progressive disease the smallest

measurements recorded since the treatment started). For patients with responding tumors who do not have objective evidence of tumor progression and are either removed from study treatment or who are given antitumor treatment other than the study treatment or who die from non-disease causes, duration of response will be censored.

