### 5.3 Duration of Therapy

In the absence of treatment delays due to adverse event(s), treatment may continue until one of the following criteria applies:

- Disease progression,
- Intercurrent illness that prevents further administration of treatment,
- Unacceptable adverse event(s),
- Patient decides to withdraw from the study,
- General or specific changes in the patient's condition render the patient unacceptable for further treatment in the judgment of the investigator,
- Clinical progression,
- Patient non-compliance
- Pregnancy
  - All women of child bearing potential (WOCBP) should be instructed to contact the investigator immediately if they suspect they might be pregnant (*e.g.*, missed or late menstrual period) at any time during study participation. Institutional policy and local regulations should determine the frequency of on study pregnancy tests for WOCBP enrolled in the study.
  - The investigator must immediately notify CTEP in the event of a confirmed pregnancy in a patient participating in the study.
- Termination of the study by sponsor.

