### 5.4 Duration of Follow Up

Patients will be followed for 4 weeks after removal from study treatment or until death, whichever occurs first. Adverse event(s) related to study treatment will be followed until resolution to a  $\leq$  grade 1 or until the adverse event remains stable at the same grade for at least 2 months.

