### 5.5 Criteria for Removal from Study

Patients will be removed from study when any of the criteria listed in Section 5.3 applies. The reason for study removal and the date the patient was removed must be documented in the Case Report Form.

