### 13.2 Sample Size/Accrual Rate

A two-stage design will be used for each group to test the null hypothesis that the extended ORR is 5% or less, versus the alternative hypothesis that the extended ORR is greater than 5% using a one-sided test with a 10% level of significance and 90% power at the alternative extended ORR of 20%. The null hypothesis of extended ORR=0.05 and the alternative extended ORR=0.20 are chosen with reference to response rate with trametinib in BRAF mutated melanoma of 22% (Flaherty *et al.*, 2012) and the response rates of single agent carfilzomib (17%) (Jagannath *et al.*, 2012) and pomalidomide (7%) (Dimopoulos *et al.*, 2012). The design is standard for such single-arm Phase II studies and appropriately minimizes the number of expected study participants when the experimental treatment is truly ineffective.

The target enrollment therefore is a minimum of 24 evaluable subjects and a maximum of 74 if both groups (biomarker positive and biomarker negative) accrue to the second stage. After testing the drug on 12 patients in each group, the trial will go to the second stage if one or more subjects respond. If the trial goes to the second stage, a total of 37 patients will be studied. If the total number of responding is more than or equal to 4, the drug is accepted. The same design as above will apply to both strata. The maximum number of this study would be 74 patients for both strata. The distribution of PFS and DOR will be summarized for each cohort using the Kaplan-Meier method. For each of these endpoints, patients will be right-censored at the date at which they were last known not to have the corresponding event.

Subjects who receive at least one dose of trametinib will be evaluable for safety. AEs will be coded according to the Medical Dictionary for Regulatory Activities (MedDRA) adverse event dictionary. The results will be tabulated to examine their frequency, organ systems affected, and relationship to study treatment. The results of laboratory assessments will be evaluated similarly. Interim safety data will be examined on an ongoing basis to ensure subject safety.

Exploratory analyses of the association of response with pharmacogenomic and pharmacodynamic will be descriptively summarized. Overall, given the limited sample size these analyses will be largely hypothesis-generating.

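### PFS may be overstated because removals for clinical progression are censored with no sensitivity analysis, and 13.2 and 13.4 give different censoring rules

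*Combined protocol and SAP*

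**What the plan says.** Section 13.4 defines PFS from the start of treatment to "the date of documented progression (based on IMWG criteria) or death due to any cause". Patients not known to have died, without objective progression, who come off study treatment or receive another antitumor treatment are handled as follows: "PFS will be censored at the last complete disease assessment". The same section adds: "Patients with two or more missing assessments immediately prior to the next visit with a documented progression will be censored for PFS", the date being the last assessment that documented no progression.

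Section 13.2 gives a shorter rule for PFS and DOR: "patients will be right-censored at the date at which they were last known not to have the corresponding event". It states no exceptions. The planned summary is also there: "The distribution of PFS and DOR will be summarized for each cohort using the Kaplan-Meier method".

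Section 5.3 lists "Clinical progression" as a reason to stop treatment, on a separate line from disease progression. Unacceptable adverse events and changes in the patient's condition are further reasons. Section 5.4 states: "Patients will be followed for 4 weeks after removal from study treatment or until death, whichever occurs first". Section 5.5 states: "The reason for study removal and the date the patient was removed must be documented in the Case Report Form".

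The Schema and section 5.1 also allow GSK2141795 to be added, after consultation, for progression that does not yet meet IMWG criteria. Section 13.4 does not say how monotherapy PFS is handled at that point. The only sub-analyses specified, in 13.5.2, concern the response rate.

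**The concern.** Kaplan-Meier treats a censored patient as having the same future hazard as those who remain at risk. A patient removed for clinical progression has just been judged to be failing, so that assumption is least credible for this patient. With follow-up ending 4 weeks after removal, a later IMWG progression or death will often go unseen. The expected direction is upward: PFS reads better than it is.

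A separate matter is that 13.2 and 13.4 do not give the same instruction. Two analysts following different sections could classify the same patient differently.

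At stake is the credibility of a named secondary objective, for each biomarker group and for the combination phase, in single-arm cohorts of 12 to 37 patients where a few removals can move the curve.

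**Working it through.** **Plan's own figure.** The documents state no PFS assumption, target or test, so there is no PFS figure to reproduce. The design figure that can be checked is the two-stage response rule in 13.2: 12 then 37 patients, continue with at least 1 response, accept with at least 4. Exact binomial calculation gives a one-sided error of 0.0935 at a 5% response rate and power of 0.9024 at 20%, which meets the stated 10% and 90%. PFS censoring does not enter that rule.

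**The two censoring rules side by side.**

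- Progression first seen after two or more missed assessments: 13.4 censors it at the last progression-free assessment. 13.2 has no such exception, so under it the progression counts.
- Censoring date: 13.4 uses the last complete disease assessment. 13.2 uses the last date known to be event-free, which could be read as a later contact.

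**Illustration of the effect of censoring clinical-only failures.**

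From the documents: disease assessments every 4 weeks (section 10), so the interval is W = 28/30.4375 = 0.920 months.

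Assumed: exponential failure times with a true median of 3 months; a share c of failures (10, 20 or 30%) recorded only as clinical progression, each censored at the previous visit; no deaths; no off-study assessment that documents progression.

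1. Hazard: λ = ln 2 / 3 = 0.2310 per month. Probability of failing in one interval: q = 1 − exp(−λW) = 0.1915.
2. Under 13.4, clinical-only failures in an interval leave the risk set at the visit before it. The estimated survival factor per visit is (1 − q)/(1 − cq).
3. Six months contains six complete intervals (6/0.920 = 6.5), so the estimate under the plan is [(1 − q)/(1 − cq)]⁶:
   - c = 10%: (0.8085/0.9809)⁶ = 0.314
   - c = 20%: (0.8085/0.9617)⁶ = 0.353
   - c = 30%: (0.8085/0.9426)⁶ = 0.398
4. With every failure counted, IMWG failures at the next visit and clinical failures when they occur, 6-month PFS is (1 − c)·exp(−6λW) + c·exp(−6λ) = (1 − c)·0.279 + c·0.250. This gives 0.276, 0.273 and 0.270.

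| Assumed share c | 6-month PFS under 13.4 | All failures counted |
|---|---|---|
| 10% | 31% | 28% |
| 20% | 35% | 27% |
| 30% | 40% | 27% |

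**Median.** Because progression is recorded on a 4-week grid, the median moves in steps. Under 13.4 the curve first falls to 50% or below at visit 4 (3.68 months) for c = 10% (0.462), and only just for c = 20% (0.4996). For c = 30% it is 0.541 at visit 4 and 0.464 at visit 5, so the median is 4.60 months, against about 3.6 with all failures counted. The median is therefore a coarse measure here.

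**Toxicity removals.** A simulation with a 4.8-month true median (the melanoma figure in 2.2.1.2, used only as a scale) gives PFS at 4.8 months of 51% with or without censoring when removal is independent of prognosis. If removed patients would have progressed about one month later, the estimate is 54% with 10% removed and 58% with 20%, against 51%. The direction depends on an association that the documents do not describe.

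**Sampling error for scale.** A binomial 95% half-width around 27% is 1.96·√(0.27·0.73/n): about 25 points for n = 12 and 14 points for n = 37.

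**The case against.** The strongest reply is that many clinical progressions would still be recorded as IMWG progression. The study calendar places a myeloma assessment and a radiologic evaluation at the off-study visit, and repeats myeloma laboratory tests at discontinuation if the last were more than 4 weeks old. The progression criteria in 11.2.2 include new or enlarging bone lesions or plasmacytomas, and hypercalcemia. Death from any cause is an event. This stands, and it makes the figures above an upper bound for each assumed share. If half of a 20% share became documented progressions, the effective share would be 10% and the estimate about 31% rather than 35%. It does not remove the problem, because 5.3 keeps clinical progression as a separate reason to stop.

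Second, requiring objective progression is a recognised choice in an open-label trial with local response review. Making an undefined clinical judgement the main event would exchange one bias for another. This also stands, so the main definition should not change.

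Third, the effect is small beside sampling error. The illustrated gaps of about 4, 8 and 13 points compare with half-widths of 14 to 25 points. That limits the practical weight, but a systematic shift does not average out and costs little to examine.

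A reader might infer three stronger conclusions that the documents do not support:

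- That the rule in 13.2 itself inflates PFS. It does not; after a gap in assessments it counts a progression that 13.4 drops. For an assessment-based endpoint, its date would ordinarily be the last progression-free assessment. The difference is an ambiguity.
- That censoring at removal for toxicity biases PFS upward. This follows only if removal is related to prognosis.
- That events after removal are discarded. Known deaths already count under 13.4, and nothing there limits assessments to those before removal.

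**Conclusion.** The concern holds in a limited form. Section 13.4 censors living patients removed for clinical progression without IMWG progression. That censoring is plausibly informative, follow-up is short, and no analysis shows how much it matters. PFS may therefore be overstated in the biomarker groups and in the combination phase. Sections 13.2 and 13.4 also need to be reconciled.

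The size cannot be derived from the documents. Under the assumed 10 to 30% shares and 3-month median, the upper bound is a 6-month PFS of about 31 to 40% against 27 to 28%, and less once off-study assessments and deaths are counted. The endpoint is secondary and summarised descriptively, and the response-rate decision is untouched. This is a low-cost improvement, not a flaw in the design.

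**What to change.** 1. Keep the IMWG-based definition in 13.4 as the main PFS analysis.
2. Pre-specify in 13.4 one sensitivity analysis that counts removal for clinical progression as an event at the recorded removal date. For monotherapy PFS, also count the addition of GSK2141795 for progression not yet meeting IMWG criteria, at its recorded date. As a worst case within that analysis, also count removal for toxicity or deterioration as an event.
3. Replace the general censoring sentence in 13.2 with a reference to 13.4, so that one rule applies, including after missed assessments.

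For removals, 5.5 already requires the reason and date on the case report form, so that part needs no new data or longer follow-up. The reason for adding GSK2141795 must be identifiable in the data. The cost is a wording change and one extra analysis. The downside is that the extra analysis uses a less objective event, which is why it stays supportive.

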**The exploratory objectives are:**

- To explore the relationship between clinical response and pharmacodynamic (PD) markers
- To explore the relationship between MAF expression and chromosomal abnormalities as determined by qPCR and FISH, respectively, and clinical response
- To explore the role of integrin  $\beta 7$  as a biomarker of MAF expression
- To explore the relationship between objective response as well as progressive disease and the tumor mutational profile
- To explore mechanism of PI3K/AKT and RAS-MEK-ERK activation and correlate these with clinical response and PD markers
- To explore the feasibility extracting cfDNA from peripheral blood and to detect RAS and RAF mutations using cfDNA

The activation state of the PI3K/AKT, RAS-MEK-ERK and additional signaling pathways pre and post-treatment will be determined by phospho-flow cytometry and RPPA and correlated with clinical response.

The level of MAF expression at baseline will be determined by qPCR. The cutoff value for the qPCR assay will be determined by calculating the median ratio and range relative copy number for 20 myeloma cell lines that are MAF positive (t(14;16) and t(4:14) cell lines) and 20 cell lines that are negative. Results of the PCR reactions will be compared to Western blot to confirm MAF expression and determine the sensitivity and specificity of the assay and its cutoff. To determine the performance of the assay in the clinical samples we will compare results obtained by qPCR to FISH data. Although this assessment will be done retrospectively, the data will be available for interim analysis for correlation with clinical response. If the data indicate that MAF may be a predictive biomarker the protocol may be modified to enrich for this subgroup of patients.

The cell surface expression of integrin  $\beta 7$  will be determined by flow cytometry on CD138 positive myeloma cells derived from screening BM samples. Correlation with MAF expression will be determined.

Next generation sequencing (Truseq or Trusight) for mutational profiling will be performed on samples obtained at screening and at progression to identify mutations that are associated with response and acquired resistance to trametinib. Although this assessment will be done retrospectively, the data will be available for interim analysis for correlation with clinical response. If the data indicate that a particular mutation and molecular pathway may be a predictive biomarker the protocol may be modified to enrich for this subgroup of patients.

The effect of trametinib on PI3K/AKT and RAS-MEK-ERK with and without the addition of

GSK2141795 evaluated by phospho-flow cytometry will be used to determine whether escape mechanisms are ERK-dependent or ERK-independent and driven by PI3K/AKT signaling. cfDNA will be extracted from peripheral blood samples. Ultra-deep sequencing will be performed on cfDNA to assess the feasibility of detecting mutations of NRAS, KRAS and BRAF from peripheral blood samples.

## **13.5 Reporting and Exclusions**

### 13.5.1 Evaluation of Toxicity

All patients will be evaluable for toxicity from the time of their first treatment with trametinib. Toxicity analyses will review adverse events, electrocardiogram results, laboratory tests (hematology, clinical chemistry, and coagulation test), vital signs and physical examinations. Safety will be measured in terms of type, frequency and severity of adverse event reactions reported according to CTCAE v4.0.

### 13.5.2 Evaluation of Response

All patients included in the study will be assessed for response to treatment, even if there are major protocol treatment deviations or if they are ineligible. Each patient will be assigned one of the following categories: 1) stringent complete response, 2) complete response, 3) very good partial response 4) partial response, 5) minimal response 6) stable disease, 7) progressive disease, 8) early death from malignant disease, 9) early death from toxicity, 10) early death because of other cause, or 11) unknown (not assessable, insufficient data).

All of the patients who met the eligibility criteria (with the possible exception of those who received no study medication) will be included in the main analysis of the response rate. Patients in response categories 7-10 should be considered to have a treatment failure (disease progression). Thus, an incorrect treatment schedule or drug administration does not result in exclusion from the analysis of the response rate.

All conclusions on treatment efficacy will be based on all eligible patients. Sub-analyses for objective response rate will be performed on all patients meeting the eligibility criteria, who have signed a consent form, and have begun study drug treatment, and had at least one follow-up assessment or progressive disease. This analysis will clearly report the reason for exclusion that may be based on major protocol deviations such as early death due to other reasons, early discontinuation of treatment, major protocol violations, etc. Further, the 95% confidence intervals will be provided.

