**The primary objective is** to evaluate the antitumor activity of trametinib determined by overall response rate (ORR), in groups of patients with relapse or refractory multiple myeloma that are:

- Biomarker positive (NRAS, KRAS, BRAF mutated as defined [Appendix F](#))
- Biomarker negative (without NRAS, KRAS, BRAF mutation)

The endpoint for the primary objective, ORR, is evidenced by confirmed response rate, defined as number of patients with partial response or better by IMWG criteria divided by the number of patients in the applicable group (biomarker positive or negative). All patients included in the study will be assessed for response to treatment, even if there are major protocol treatment deviations or if they are ineligible (see section 13.5.2). The patient will be classified as having had a response if he/she has a confirmed response per the definitions in section [11.2.2](#). (i.e., a stringent complete response, or complete response or near complete response or very good partial response or partial response noted as the objective status of two consecutive assessments). The rate of minor response (MR) and progressive disease (PD) will also be observed.

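### Does the plan need a two-stage p-value and an interval matched to its one-sided 10% test of the response rate?

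*Combined protocol and SAP*

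**What the plan says.** Section 13.2 sets the same test in each biomarker group: a response rate of 5% or less against a target of 20%, "using a one-sided test with a 10% level of significance" and 90% power. The rule is written in counts. After 12 patients, "the trial will go to the second stage if one or more subjects respond". After 37, "If the total number of responding is more than or equal to 4, the drug is accepted".

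Section 13.5.2 names the analysis set: "All conclusions on treatment efficacy will be based on all eligible patients". A paragraph on further analyses follows: "Sub-analyses for objective response rate will be performed on all patients meeting the eligibility criteria", with conditions on consent, treatment and follow-up. That paragraph ends with the only statement about intervals for the response rate: "Further, the 95% confidence intervals will be provided". It gives no method, does not mention the stage 1 stop, and does not say whether the main analysis is covered. No p-value is planned anywhere in section 13.

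**The concern.** Three things look out of step. The test is one-sided at 10%, so the matching interval is a one-sided 90% lower bound (equivalently, a two-sided 80% interval), but the plan asks for 95%. The design can stop at 0/12, but nothing says the interval will allow for that. The interval sentence also sits among the sub-analyses, while efficacy conclusions rest on the main analysis.

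The visible consequence is at the acceptance boundary. A group accepted with exactly 4/37 could be published beside a conventional exact p-value above 0.10 and an interval that contains 5%. A reader might think that the trial had contradicted itself. A reader who judged activity by whether an exact 95% interval excludes 5% would in effect require 6 responses, a much stricter rule than the one designed.

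**Working it through.** **Inputs (section 13.2).** Null rate 0.05; alternative 0.20; 12 patients in stage 1, 25 more in stage 2; continue at 1 or more responses; accept at 4 or more of 37.

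**1. Reproduce the design.** With X₁ ~ Bin(12, p) and X₂ ~ Bin(25, p),

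P(accept | p) = Σ over x = 1 to 12 of P(X₁ = x) · P(X₂ ≥ 4 − x).

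At p = 0.05:

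| x | P(X₁ = x) | P(X₂ ≥ 4 − x) | product |
|---|---|---|---|
| 1 | 0.3413 | 0.1271 | 0.0434 |
| 2 | 0.0988 | 0.3576 | 0.0353 |
| 3 | 0.0173 | 0.7226 | 0.0125 |
| 4 or more | 0.0022 | 1 | 0.0022 |

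The sum is 0.0935 (unrounded 0.09347). The same sum at p = 0.20 is 0.902. Both meet the stated 10% and 90%. The chance of stopping at stage 1 under the null is 0.95¹² = 0.540, and the expected size is 12 + 25 × 0.460 = 23.5. The stated design reproduces.

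**2. Where 0.112 comes from.** The single-stage tail P(Bin(37, 0.05) ≥ 4) is 0.1119. It exceeds 0.0935 because it counts paths with 0/12 and then at least 4/25, which this design cannot produce: 0.5404 × 0.0341 = 0.0184, and 0.0935 + 0.0184 = 0.1119. The single-stage figure is therefore the wrong tail for this design.

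**3. Exact tail probabilities and intervals by final count.** The two-stage limits invert the tail probability in step 1, ordering outcomes by stage and then by total.

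| Outcome | Single-stage p | Two-stage p | Clopper-Pearson 95% | Two-stage 95% |
|---|---|---|---|---|
| 4/37 | 0.112 | 0.0935 | 3.0–25.4% | 3.2–28.5% |
| 5/37 | 0.036 | 0.032 | 4.5–28.8% | 4.7–30.5% |
| 6/37 | 0.0095 | 0.0089 | 6.2–32.0% | 6.3–33.0% |

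The p-value conflict is confined to 4/37. At 95%, both exact intervals contain 5% at 4/37 and at 5/37, so the two-stage calculation does not alter that picture. At 5/37 the result depends on the method: the Wilson lower limit is 5.9% and the mid-P limit 5.1%. At the matched 80% level and 4/37, Clopper-Pearson gives 4.8–20.5% and the two-stage interval 5.1–22.0%; only the second agrees with acceptance.

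**4. How often the boundary arises.** P(exactly 4/37) ÷ P(accept) is 0.165/0.447 = 37% at a true rate of 10%, 0.127/0.751 = 17% at 15%, and 0.054/0.902 = 6% at 20%.

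**5. Coverage at the planned level.** Over true rates from 0.5% to 60%, plain 95% Clopper-Pearson under this design covers at least 94.1% (minimum near 26.5%). The shortfall is 0.9 points at worst.

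**6. What two-stage intervals would cost.** 95% upper limits:

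| Outcome | Clopper-Pearson | Two-stage |
|---|---|---|
| 1/37 | 14.2% | 26.5% |
| 2/37 | 18.2% | 26.6% |
| 3/37 | 21.9% | 27.2% |

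A group stopped at 0/12 has an exact upper limit of 1 − 0.025^(1/12) = 26.5%, so 1/37 would be reported as hardly more informative than 0/12. At 1/37 and 2/37 the plain interval excludes the 20% alternative; the two-stage interval does not.

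**The case for a change.** The best argument for a change is that leaving the method open lets it be chosen after the data are seen. At 4/37 and the 80% level that choice matters: Clopper-Pearson (4.8%) and Wald (4.3%) have lower limits below 5%, while Wilson (5.9%), Jeffreys (5.7%), Agresti-Coull (5.7%) and mid-P (5.6%) lie above it. The two-stage 80% interval reproduces the protocol's own level and power. By contrast, requiring an exact 95% lower limit above 5% amounts to requiring 6/37, with level 0.009 and power 0.751. The boundary result is not rare if the true rate is near 10%, and two groups are tested. A few sentences would settle it.

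The arithmetic stands, and so does the observation that the method and analysis set for the interval are unstated. The rest has less force. The 80% interval is not in the plan, so the spread of methods at that level affects nothing that will be reported. At 95%, every one of those methods contains 5% at 4/37. The stricter rules describe a use of the interval that the protocol never proposes. A two-stage interval is also not a free gain: it loses precision at the low counts where a phase II trial needs to show inactivity. Text fixed at 12 then 25 patients would also need a rule for other realised numbers, because the eligible set in section 13.5.2 may differ from 37.

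**Conclusion.** No change is needed. Followed as written, the plan gives a sound accept-or-reject decision in each group: the count decides, with level 0.0935 and power 0.902, and neither depends on how an interval is calculated. A 95% interval beside a one-sided 10% screening rule is ordinary descriptive reporting. That it contains 5% at 4/37, and for exact methods at 5/37, reflects the different confidence level and is not a contradiction.

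The remaining gap is that the interval method and its analysis set are not named. An analyst can fill it sensibly by reporting an exact 95% interval for the main analysis, naming the method and calling it descriptive. If a p-value is wanted at 4/37, the one that belongs to this design is 0.0935, with a one-sided 90% lower bound of 5.1%. Either choice of 95% interval is defensible: the plain one under-covers by at most 0.9 points, and the two-stage one has much higher upper limits at 1 to 3 responses.

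This rests on two assumptions: acceptance is judged only by the count in section 13.2, and the realised numbers are 12 and 25. With other numbers the figures shift somewhat, but the reasoning holds.
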